## 6.0 DATA AND SPECIMEN SUBMISSION

### 6.1 Data collection and submission

Medidata Rave is the clinical data management system being used for data collection for this trial/study. Access to the trial in Rave is controlled through the CTEP-IAM system and role assignments.

Requirements to access Rave via iMedidata:

- A valid CTEP-IAM account and linked ID.me account (ID.me accounts are required for all newly created CTEP-IAM accounts and by July 1, 2023 for all users); and
- Assigned a Rave role on the LPO or PO roster at the enrolling site of: Rave CRA, Rave Read Only, Rave CRA (LabAdmin), Rave SLA, or Rave Investigator.

Rave role requirements:

- Rave CRA or Rave CRA (Lab Admin) role must have a minimum of an Associate Plus (AP) registration type;
- Rave Investigator role must be registered as an Non-Physician Investigator (NPiVR) or Investigator (iVR); and
- Rave Read Only or Rave SLA role must have at a minimum an Associate (A) registration type.

Refer to [REDACTED] for registration types and documentation required.

Upon initial site registration approval for the study in the [REDACTED] application, all persons with Rave roles assigned on the appropriate roster will be sent a study invitation email from iMedidata. To accept the invitation, site staff must either click on the link in the email or log in to iMedidata via the CTSU members' website under Data Management > Rave Home and click to accept the invitation in the Tasks pane located in the upper right corner of the iMedidata screen. Site staff will not be able to access the study in Rave until all required Medidata and study-specific trainings are completed. Trainings will be in the form of electronic learnings (eLearnings) and can be accessed by clicking on the eLearning link in the Tasks pane located in the upper right corner of the iMedidata screen. If an eLearning is required for a study and has not yet been taken, the link to the eLearning will appear under the study name in the Studies pane located in the center of the iMedidata screen; once the successful completion of the eLearning has been recorded, access to the study in Rave will be granted, and a Rave EDC link will replace the eLearning link under the study name.

Site staff who have not previously activated their iMedidata/Rave account at the time of initial site registration approval for the study in the [REDACTED] application will receive a separate invitation from iMedidata to activate their account. Account activation instructions are located on the CTSU website in the Data Management section under the Rave resource materials (Medidata Account Activation and Study Invitation Acceptance). Additional information on iMedidata/Rave is available on the CTSU members' website in the Data Management > Rave section or by contacting the CTSU Help Desk at [REDACTED]

#### 6.1.1 Supporting documentation

This study requires supporting documentation for diagnosis, response and progression. Supporting documentation must be deidentified and submitted via Rave at the timepoints below:

**Baseline:** Imaging report, pathology report, operative report, clinic note, standard visual field report, and Central Pathology & BRAF Results Form

**During Treatment & Follow-up:** Visual field testing reports must be submitted at each timepoint specified in [Section 5.0](#). For any subsequent treatment received for patients on Cohort A and Cohort B, surgical, radiation planning and radiology reports must be submitted.

**Response:** Imaging report

**Progression:** Imaging report, and pathology report if applicable

### 6.1.2 Data Quality Portal

The Data Quality Portal (DQP) provides a central location for site staff to manage unanswered queries and form delinquencies, monitor data quality and timeliness, generate reports, and review metrics.

The DQP is located on the CTSU members' website under Data Management. The Rave Home section displays a table providing summary counts of Total Delinquencies and Total Queries. DQP Queries, DQP Delinquent Forms, DQP Form Status and the DQP Reports modules are available to access details and reports of unanswered queries, delinquent forms, forms with current status, and timeliness reports. Site staff should review the DQP modules on a regular basis to manage specified queries and delinquent forms.

The DQP is accessible by site staff who are rostered to a site and have access to the CTSU website. Staff who have Rave study access can access the Rave study data via direct links available in the DQP modules.

CTSU Delinquency Notification emails are sent to primary contacts at sites twice a month. These notifications serve as alerts that queries and/or delinquent forms require site review, providing a summary count of queries and delinquent forms for each Rave study that a site is participating in. Additional site staff can subscribe and unsubscribe to these notifications using the CTSU Report and Information Subscription Portal on the CTSU members' website.

To learn more about DQP use and access, click on the Help Topics button displayed on the Rave Home, DQP Queries, DQP Delinquent Forms, DQP Form Status, and DQP Reports modules.

Note: Some Rave protocols may not have delinquent form details or reports specified on the DQP. A protocol must have the Calendar functionality implemented in Rave by the Lead Protocol Organization for delinquent form details and reports to be available on the DQP. Site staff should contact the LPO Data Manager for their protocol regarding questions about Rave Calendaring functionality.

### 6.1.3 IRB Terminations

Until institutions receive a formal notice from the Alliance regarding termination to patient follow-up, institutions must not close this trial with the IRB of record for the study. Please contact the Alliance Regulatory team at [REDACTED] with any questions.

## 6.2 Specimen collection and submission

### 6.2.1 Real time histopathology review and BRAF IHC testing (mandatory for all patients)

Real-time histopathology review and BRAF IHC testing will be conducted on tissue from the diagnostic or recurrent biopsies and/or surgery at Dana-Farber Cancer Institute/BWH (CLIA-certified laboratory, #22D0705149). **The submission of these samples for**

**histopathology review is required for all patients pre-registered to this study, including those who are found to be ineligible and those who do not receive protocol therapy.** Beta-catenin IHC will testing will also be performed for eligibility screening on the BRAF IHC inconclusive cases. Slides must be shipped within 28 days after patient pre-registration.

Slides must be accompanied by a completed “Central Pathology and BRAF Results Form” found on the A071601 study page on the CTSU and Alliance web sites. Failure to submit this form with the specimens will delay turnaround time for central review and biomarker testing. See [Section 4.3](#) and [4.4](#) for specific instructions and process for central review results/registration reporting.

Please note that slides must also be accompanied by a de-identified surgical pathology report.

### 6.2.2 A071601-ST1 (optional for patients)

All participating institutions must ask patients for their consent to participate in the correlative substudies planned for Alliance A071601-ST1, although patient participation is optional. For patients who consent to participate (model consent question, “I agree to have my blood collected and tissue submitted, and I agree that my specimen sample(s) and related information may be used for the laboratory study described above”), 1 FFPE tumor block (or slide alternatives) and will be submitted from surgeries performed prior to treatment and at recurrence and progression. Paraffin blocks or slides comprised of primary and, when available, metastatic tissue should be submitted. Whole blood will also be collected and submitted. Blocks/slide and whole blood to be used for biomarker studies as described in [Section 14.1](#).

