### Pre-Study Testing Intervals

- To be completed  $\leq 28$  DAYS before registration:
  - All laboratory studies, history and physical, eye exam
  - Any scan which is utilized for tumor measurement per protocol.
- To be completed  $\leq 60$  DAYS before registration: Any baseline exams used for screening that are not utilized for tumor measurement.

	Prior to Registration*	Day 1 of each cycle (cycle is 28 days)*	Weekly on treatment	Every 2 cycles	Monthly on treatment	Post treatment followup**	Clinical & survival follow- up ***
Tests & Observations							
History and physical, weight, PS	X(1)	X(1)				X(1)	X(1)
Height	X						
Pulse, Blood Pressure	X	X					X
Registration Fatigue/Uniscale Assessment	X(2)						
Adverse Event Assessment	X(3)	X(3)				X(3)	X(3)
EKG		B					
Echo or MUGA		C					
O2 Saturation		X(8)					
Eye exam	A	A				A	
Skin Exam		D					D
Patient Medication Diary		X(9)					
Laboratory Studies							
Complete Blood Count, Differential, Platelets	X	X					
Electrolytes, Creatinine (BMP)			X (10)				
Endocrine evaluation (with labs as necessary per endocrine evaluation)					X		
Chemistry	X(4)	X(4)				X(4)	
Serum or Urine HCG	X(5)						
Staging							
Central review for eligibility (pathology/BRAF)	X(6)						
MRI/CT Brain	X (7)			E(7)		E(7)	E(7)

Correlative studies: For patients who consent to participate in A071601-ST1				
Tissue block or slides				Archival tissue at baseline, recurrence and progression for banking and correlative science, see Section 6.2 .
Whole blood samples				Whole blood at prior to treatment, Day 1 of Cycle 3 (+/- 3 days), end of treatment, recurrence and progression, see Section 6.2 .

- \* Labs completed prior to registration may be used for day 1 of cycle 1 tests if obtained  $\leq 14$  days prior to treatment. For subsequent cycles, labs, tests and observations may be obtained +/- 3 days from scheduled day of assessment. Radiographic windows are +/- 7 days from scheduled day of assessment (except prior to registration). A new cycle is defined by day 1 on which the patient starts drug for that cycle.
- \*\* Physical examination, adverse event assessment, medication diary, and chemistry are required 4 weeks (+/- 7 days) after the end of treatment. End of treatment is considered 4-5 cycles of treatment, or end of treatment with vemurafenib + cobimetinib.

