### 6.2.4 Overview of specimen requirements

	≤ 28 days after pre- registration	Prior to Protocol Tx	Day 1 of Cycle 3 (+/- 3 days)	End of Protocol Tx	At recurrence and progression
Mandatory for all patients pre-registered to A071601:					
1 H&E slide and 2 unstained slides for histopathology review & BRAF IHC testing	X				
For patients registered to A071601-ST1A, submit the following:					
Paraffin block or alternative from surgery		X 			X 
Whole blood  (EDTA/lavender top)		10 mL			
Whole Blood		20 mL	20 mL	20 mL	20 mL

(EDTA/lavender top)					
---------------------	--	--	--	--	--

- 1 For patients who consent to question “I agree to have my blood collected and tissue submitted, and I agree that my specimen sample(s) and related information may be used for the laboratory study described above.” Blocks/slide and whole blood to be used for biomarker studies as described in [Section 14.1](#).
- 2 Paraffin block or alternatives may be sent up 6 months after registration (for pre-tx specimen) and up to 6 months after progression (for progression/recurrent specimens).

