#### 14.1 Identification of blood and tissue-based molecular biomarkers (A071601-ST1)

##### 14.1.1 Background

Our goal is to identify blood and tissue-based molecular biomarkers of therapeutic response in patients with papillary craniopharyngioma tumors that are simultaneously treated with inhibitors of BRAF and MEK. Our group recently published a whole-exome and targeted sequencing study in craniopharyngiomas, where we identified recurrent BRAF mutations in papillary craniopharyngiomas and recurrent beta-catenin mutations in adamantinomatous craniopharyngiomas. The vast majority of papillary craniopharyngioma cases (~95%) harbored the oncogenic BRAF V600E mutation. In the correlative analyses for this clinical trial we propose to perform several genome wide analyses on craniopharyngioma samples. If normal patient DNA is available, we will perform whole exome sequencing on these samples. If normal patient DNA is unavailable we will perform targeted sequencing that is limited to roughly 500 cancer-associated genes. Transcriptome analysis will be performed on all samples where there is sufficient tissue. Common mechanisms of resistance have been reported in other cancers treated with BRAF/MEK inhibition. This data will help us to identify genetic biomarkers of response and of resistance. These studies could provide suggestions as to other therapies that might aid tumors that do not respond to BRAF and MEK inhibition. We will also perform pharmacodynamics studies prior to and after treatment using immunohistochemical analysis, to assess evidence of MAPK pathway activation pre- and post-treatment with vemurafenib + cobimetinib combination.

Furthermore, using an assay which has been well-validated in melanoma patients, we recently detected circulating BRAF V600E mutation in the blood of a patient with a papillary craniopharyngioma. We hope to validate the utility of this test through analysis of blood collected in this trial. We will assess whether the circulating BRAF V600E assay can be used to predict which patients have a papillary craniopharyngioma (i.e. ‘liquid

biopsy'), and whether the levels of circulating BRAF V600E correlates with response to therapy.

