We also propose to perform either whole exome, transcriptome sequencing or targeted sequencing of 500 cancer associated genes on post-treatment resection samples – on either residual tissue samples that are resected following a successful initial course of treatment or on recurrence samples that regrow following termination of treatment or while on treatment. We hope to identify mechanisms of resistance in those samples.

We may also perform immunofluorescence characterization of tissue pre- and post-treatment using a range of markers to characterize cell cycle status, relevant cell signaling pathways, immune infiltrates and other possibly relevant markers as outlined below.

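### The protocol's tissue schedule has no time point for surgery after treatment without progression, although Section 14.1 plans to analyse that tissue

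*Combined protocol and SAP*

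**What the plan says.** Three places set the tissue time points for A071601-ST1, and they agree.

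- Section 6.2.2: the block or slides "will be submitted from surgeries performed prior to treatment and at recurrence and progression".
- Section 5.0, correlative rows of the calendar: "Archival tissue at baseline, recurrence and progression for banking and correlative science".
- Section 6.2.4 table: tissue is marked before protocol treatment and at recurrence and progression. The end-of-treatment column lists whole blood but no tissue. Footnote 2 gives two shipping windows, one counted from registration for pre-treatment specimens and the other running "up to 6 months after progression (for progression/recurrent specimens").

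Section 14.1.1 describes a wider set of specimens. Post-treatment sequencing is to be done on "residual tissue samples that are resected following a successful initial course of treatment or on recurrence samples that regrow", so the two types are named separately. The same section plans "pharmacodynamics studies prior to and after treatment using immunohistochemical analysis", with the aim "to assess evidence of MAPK pathway activation pre- and post-treatment with vemurafenib + cobimetinib combination". It adds: "We may also perform immunofluorescence characterization of tissue pre- and post-treatment". Section 14.1.2 describes tissue changes seen in the first treated patient and commits to looking for them in resected tumours.

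Section 7.1.1 directs Cohort A to definitive surgery or radiation after four cycles. Complete responders go to radiation. For the others the treating physician chooses surgery, radiation or both. Section 7.1.2 allows discretionary surgery in Cohort B after four cycles.

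**The concern.** The substudy names a specimen type that the collection schedule does not request. A site following Sections 5.0 and 6.2 would send tissue from before treatment and from a recurrence or progression. It would have no instruction to send tissue from an operation on a tumour that shrank or stayed stable.

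This bears on interpretation as well as on the number of samples. If the only scheduled post-drug tissue comes from tumours that grew again, the post-treatment half of any before-and-after comparison is selected on outcome. A responder would contribute to it only after recurring or progressing, and a responder who stays controlled would contribute nothing. Changes in MAPK signalling, immune infiltrate or histology caused by the drug could not be separated cleanly from changes that accompany regrowth. Residual tumour removed soon after a successful course is the specimen best placed to separate them, and Section 14.1.1 asks for it by name.

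**Working it through.** The plan states no figure on this point, so the check sets the passages side by side.

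**Step 1. What is scheduled (Sections 5.0, 6.2.2 and 6.2.4).**

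| Time point | ST1 tissue | ST1 whole blood |
|---|---|---|
| Before protocol treatment | yes | yes |
| Day 1 of Cycle 3 | no | yes |
| End of protocol treatment | no | yes |
| Recurrence and progression | yes | yes |

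Tissue has two time points and blood has four. Because all three places agree, a broken table does not explain the gap.

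**Step 2. What Section 14.1 needs, and whether a time point supplies it.**

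| Planned use | Tissue needed | Scheduled source |
|---|---|---|
| Baseline biomarkers, responders against non-responders (14.1.3) | pre-treatment | yes |
| Sequencing of recurrence samples, on or off drug (14.1.1) | recurrence or progression | yes |
| Sequencing of residual tumour after a successful course (14.1.1) | resection without progression | none |
| Before-and-after MAPK immunohistochemistry (14.1.1) | pre-treatment and post-treatment | only where the tumour recurred or progressed |
| Histology and staining of treated tumours (14.1.2) | post-treatment | only where the tumour recurred or progressed |

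**Step 3. Whether such operations are expected.** They are.

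- Section 12.1.1 sends Cohort A patients in complete response, partial response or stable disease on to radiation, surgery or both, by way of Section 7.1.1.
- Footnote E of Section 5.0 allows surgery to be put off by up to 4 weeks so that a confirmatory scan can document a response. The protocol thus foresees operating on responders.
- Section 6.1.1 requires surgical, radiation-planning and radiology reports for any later treatment in both cohorts. It does not ask for tissue.

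**Step 4. How many patients.** Section 13.3.1 plans 16 evaluable patients per cohort plus 2 for ineligibility or cancellation: 16 + 2 = 18 in Cohort A. From those 18, remove the patients who cannot lose tissue through this gap:

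- complete responders, who go to radiation;
- patients who progress, whose tissue is already scheduled;
- patients given radiation alone;
- patients who decline ST1.

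The documents give no expected share for any of these groups, so the remainder cannot be computed. It is fewer than 18, plus any Cohort B patient operated on without progression.

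**The case against.** The strongest reply is that Section 14.1 is exploratory and takes what tissue it can get. Transcriptome work depends on sufficient tissue, immunofluorescence is optional, and histology uses whatever samples are available. Section 14.1.3 is explicit that the aim is to generate hypotheses. Patients may decline ST1, and no primary or secondary endpoint uses this tissue. All of that stands, and it limits the weight of the point. It does not explain why a specimen type named in Section 14.1.1 has no place in the collection schedule.

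Four stronger readings are tempting, and the documents do not support them.

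- **That this tissue is never collected.** The evidence shows only that the protocol's own schedule does not call for it. Nothing forbids sending it, and the consent question quoted in Section 6.2.2 sets no time limit. Section 6.2.3 refers to a Correlative Science Manual that is not among the documents. If the manual does request the tissue, it goes beyond the requirements table in Section 6.2.4, and the two need to be aligned.
- **That before-and-after comparison is impossible.** Section 14.1.1 accepts either residual or recurrence samples, and the second kind is scheduled. Patients who recur or progress can still supply a pair.
- **That the remaining post-drug tissue is all drug-resistant.** Section 14.1.1 includes tumours that regrow after treatment has ended, and Cohort A ordinarily stops after four cycles. Regrowth off drug is not necessarily resistance.
- **That 16 to 18 Cohort A patients are lost.** That range counts patients who cannot be affected, as Step 4 shows.

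**Conclusion.** The inconsistency between Sections 5.0 and 6.2 and Section 14.1 is real and should be corrected. As written, resection without progression has no tissue time point. Scheduled post-drug tissue comes only from tumours that recurred or progressed, which selects on outcome and omits residual tumour taken soon after treatment in responders.

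The effect is limited. It falls on ST1-consenting, non-progressing patients who have surgery, a number the documents do not give. It touches the exploratory correlative objective 2.4.1 and leaves the primary and secondary endpoints alone. The baseline responder against non-responder analysis is intact, and so are the recurrence and progression comparisons. In a trial of at most 36 planned patients, though, each such specimen is hard to replace.

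The conclusion assumes that sites follow the protocol's schedule and that the manual, which could not be checked, does not already request this tissue.

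**What to change.** Add one tissue time point to Section 6.2.2, the Section 6.2.4 table and the Section 5.0 calendar: any tumour resection after the start of protocol treatment, whether or not progression has occurred.

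Extend footnote 2 of Section 6.2.4 with a submission window counted from the date of surgery, for example up to 6 months. The existing windows cannot simply be reused. They count from registration for pre-treatment specimens and from progression for later ones, and surgery without progression has no progression date.

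Check that the ST1 consent and the Correlative Science Manual cover the new time point; neither could be verified here. If the sponsor does not want this tissue, the alternative is to narrow Section 14.1 to pre-treatment and recurrence or progression specimens, so that the two parts agree.

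The cost is small: a short amendment, then retrieving and shipping a block or slides from operations already being done. No extra procedure is needed.

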### 6.2.3 Correlative Science Manual (CSM)

The Alliance A071601 Correlative Science Manual (CSM) contains instructions for specimen collection, processing and shipping. The manual can be found on the BioMS, CTSU, and CTSU websites. Questions regarding the CSM should be addressed to the contacts specified in the manual.

### 6.2.4 Overview of specimen requirements

	≤ 28 days after pre- registration	Prior to Protocol Tx	Day 1 of Cycle 3 (+/- 3 days)	End of Protocol Tx	At recurrence and progression
Mandatory for all patients pre-registered to A071601:					
1 H&E slide and 2 unstained slides for histopathology review & BRAF IHC testing	X				
For patients registered to A071601-ST1A, submit the following:					
Paraffin block or alternative from surgery		X 			X 
Whole blood  (EDTA/lavender top)		10 mL			
Whole Blood		20 mL	20 mL	20 mL	20 mL

(EDTA/lavender top)					
---------------------	--	--	--	--	--

- 1 For patients who consent to question “I agree to have my blood collected and tissue submitted, and I agree that my specimen sample(s) and related information may be used for the laboratory study described above.” Blocks/slide and whole blood to be used for biomarker studies as described in [Section 14.1](#).
- 2 Paraffin block or alternatives may be sent up 6 months after registration (for pre-tx specimen) and up to 6 months after progression (for progression/recurrent specimens).

